# 5.2.2. LDV/SOF FDC Packaging and Labeling

LDV/SOF FDC tablets are packaged in white, high density polyethylene (HDPE) bottles. Each bottle contains 30 tablets, a silica gel desiccant and polyester packing material. Each bottle is enclosed with a white, continuous thread, child-resistant screw cap with an induction-sealed, aluminum-faced liner.

LDV/SOF FDC bottles to be distributed to centers in Japan shall be labeled for clinical use to meet applicable requirements of the Pharmaceuticals and Medical Devices Agency (PMDA), Japan, and/or other local regulations as applicable.

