#### 5.3.2. SOF Packaging and Labeling

SOF tablets are packaged in white, high density polyethylene (HDPE) bottles. Each bottle contains 30 tablets, a silica gel desiccant and polyester packing material. Each bottle is enclosed with a white, continuous thread, child-resistant screw cap with an induction-sealed, aluminum-faced liner.

SOF bottles to be distributed to centers in Japan shall be labeled for clinical use to meet applicable requirements of the Pharmaceuticals and Medical Devices Agency (PMDA), Japan, and/or other local regulations as applicable.

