#### 5.6. Study Drug Adherence and Drug Accountability

Subjects must be instructed to bring back all study medication(s) in the original container at every study visit after Day 1 through the end of treatment.

Study medication(s) will be reconciled using medication pill count at every post-Day 1 visit by the investigator or designee (ie, pharmacist) in order to monitor the subject's adherence with the medication regimen.

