### **3.4. Examination of Subject Subsets**

Subsetting of subjects based on randomization stratification factors will be explored for subgroup analyses. If there are discrepancies in stratification factor values between the IWRS and the clinical database, the values recorded in the clinical database will be used for analyses.

Other subject subsets will also be explored for the primary efficacy endpoint (SVR12), including the following:

- age (< 65 years,  $\geq$  65 years)
- sex (male, female)
- baseline BMI ( $< 25 \text{ kg/m}^2$ ,  $\geq 25 \text{ kg/m}^2$ )
- HCV genotype subtype (if applicable)
- cirrhosis (cirrhosis, absence of cirrhosis, missing)

- IL28B (CC, non-CC; with non-CC further broken down to CT, TT)
- Baseline HCV RNA (< 800,000 IU/mL,  $\geq$  800,000 IU/mL, and  $< 5 \log_{10}$  IU/mL,  $\geq 5 \log_{10}$  IU/mL)
- baseline alanine aminotransferase (ALT) ( $\leq 1.5 \times$  upper limit of normal [ULN],  $> 1.5 \times$  ULN)
- prior HCV treatment experience (treatment naive, treatment-experienced)
- most recent prior HCV treatment response (non-responder, relapse/breakthrough, early treatment discontinuation, met a virologic stopping rule, not otherwise listed, unknown) for treatment-experienced subjects
- completed study treatment, discontinued study treatment
- adherence to study regimen (<80%,  $\geq$  80%)

The primary efficacy endpoint for Cohort 2 will be examined using the applicable subsets above.

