#### **4.2.2. Adherence to Study Drug**

The total number of tablets administered will be summarized using descriptive statistics (n, mean, SD, median, Q1, Q3, minimum, and maximum).

The presumed total number of tablets administered to a subject will be determined by the data collected on the drug accountability CRF using the following formula:

$$\begin{aligned} \text{Total Number of Doses Administered} = \\ (\sum \text{No. of Tablets Dispensed}) - (\sum \text{No. of Tablets not administered}) \end{aligned}$$

The level of adherence to the study drug regimen will be assessed based on the total amount of study drug administered relative to the total amount of study drug prescribed at baseline.

The level of adherence will be expressed in percentage using the following formula:

$$\text{Level of Adherence (\%)} = \left( \frac{\text{Total Amount of Study Drug Administered}}{\text{Total Amount of Study Drug Prescribed at baseline}} \right) \times 100$$

Note: If calculated adherence is greater than 100%, the result will be set to 100%.

In Cohort 1, for Group 1, the total amount of LDV/SOF (90 mg/400 mg) prescribed for 12 weeks would require 84 tablets; for Group 2, the total amount of SOF (400 mg) prescribed for 12 weeks would require 84 tablets and weight-based RBV (200 mg) prescribed for 12 weeks would require 252 (3 tablets/day for baseline weight  $\leq$  60 kg) or 336 (4 tablets/day for baseline weight  $>$  60 kg to  $\leq$  80 kg) tablets or 420 (5 tablets/day for baseline weight  $>$  80 kg) tablets.

In Cohort 2, the total amount of LDV/SOF (90 mg/400 mg) prescribed for 12 weeks would require 84 tablets.

Subjects who prematurely discontinue study drug for lack of efficacy (ie, virologic failure) will have the total amount of study drug prescribed calculated up to the first date when virologic failure criteria were met. For virologic failure confirmed by 2 consecutive measurements the date of the first measurement will be used. If there are study drug bottles dispensed on or after the subject first met virologic failure criteria, these bottles will not be included in the calculation of adherence. If a bottle is dispensed and the bottle is returned empty, then the number of tablets returned will be entered as zero. If a bottle is dispensed but not returned (missing), the number of tablets taken from that bottle will be counted as zero.

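### An unreturned bottle counts as zero tablets taken despite pill counts at every visit, so one missing bottle puts a fully adherent subject at about 67%, below the 80% cut

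*SAP*

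**What the plan says.** SAP 4.2.2 computes adherence from the drug accountability CRF as the amount administered divided by the amount prescribed at baseline, capped at 100%. For LDV/SOF, "the total amount of LDV/SOF (90 mg/400 mg) prescribed for 12 weeks would require 84 tablets"; for the comparator, "the total amount of SOF (400 mg) prescribed for 12 weeks would require 84 tablets". The only reduction of the denominator that it describes is for subjects who stop because of virologic failure.

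Two rules for bottles follow. A bottle returned empty has zero tablets returned, so all its tablets count as taken. For a bottle that does not come back: "If a bottle is dispensed but not returned (missing), the number of tablets taken from that bottle will be counted as zero".

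Protocol 5.6 has subjects bring all medication back in the original container at every visit after Day 1, where it is "reconciled using medication pill count at every post-Day 1 visit". Protocol Appendix 2 places those visits at Weeks 1, 2, 3, 4, 5, 6, 8, 10 and 12, and dispensing at Day 1, Week 4 and Week 8. LDV/SOF and SOF both come in 30-tablet bottles (Protocol 5.2.2 and 5.3.2). RBV comes in 140-capsule blister packaging (Protocol 5.4.2).

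The result is used in three places: the adherence categories and the display of subjects at 80% or more on every study drug (both SAP 4.2.2), and the SVR12 subgroups, where "adherence to study regimen" is split at 80% (SAP 3.4).

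**The concern.** The rule gives very different scores to the same dosing. An emptied bottle handed back is credited with 30 tablets. The same bottle left at home or thrown away is credited with none, even if site staff had already counted it at one or more visits.

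Because a bottle holds about a third of the course, a single missing one decides the subject's category. The adherence table would then partly measure container return rather than drug taking. The below-80% SVR12 subgroup would mix subjects who were under-dosed with subjects who were fully dosed. It would also disagree with SAP 4.2.1, which measures duration of exposure by dose dates: the same subject can show 12 weeks of exposure and 67% adherence in one report.

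**Working it through.** **Inputs.** Prescribed amounts: SAP 4.2.2. Bottle size: "LDV/SOF FDC tablets are packaged in white, high density polyethylene (HDPE) bottles. Each bottle contains 30 tablets", and the same for SOF. Dispensing and visit schedule, with windows of ±3 days: Protocol Appendix 2. One bottle per dispensing is inferred from 30 tablets for 28 days; the documents do not state it.

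**1. The plan's own denominators.** Units per day × 7 × 12: 1 × 84 = 84 for LDV/SOF and for SOF; 3 × 84 = 252, 4 × 84 = 336 and 5 × 84 = 420 for RBV. All agree with SAP 4.2.2.

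**2. One bottle missing, every dose taken, 28 tablets from each bottle.** Dispensed: 3 × 30 = 90. Not administered under the rule: 30 for the missing bottle plus 2 left in each of the others, 30 + 2 + 2 = 34. Adherence = (90 − 34)/84 = 56/84 = 66.7%.

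**3. Range.** Three bottles hold 90 tablets and 84 are taken, so any one bottle supplies at least 84 − 60 = 24 and at most 30.
- 24 from the missing bottle: 60/84 = 71.4%
- 30 from the missing bottle: 54/84 = 64.3%

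**4. Against the 80% cut.** 20% of 84 is 16.8, so 17 uncredited tablets are enough to fall below 80% (67/84 = 79.8%). The minimum in step 3 is 24, so the subject is always below the cut.

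**5. Crediting the last recorded count, nominal visit days.**

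| Missing bottle | Last count before its final return visit | Credited from it | Adherence |
|---|---|---|---|
| First | Week 3 | 21 | (56 + 21)/84 = 77/84 = 91.7% |
| Second | Week 6 | 14 | (56 + 14)/84 = 70/84 = 83.3% |
| Third | Week 10 | 14 | (56 + 14)/84 = 70/84 = 83.3% |

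**6. The same within the ±3-day windows.**
- Worst case, second bottle: Week 4 visit on Day 29, Week 6 on Day 39, Week 8 on Day 59. The bottle supplied 30 tablets, of which 10 had been counted: (84 − 30 + 10)/84 = 64/84 = 76.2%.
- Best case, first bottle: Week 3 on Day 24, Week 4 on Day 25. It supplied 24, of which 23 had been counted: 83/84 = 98.8%.

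**7. Scale.** With 100 subjects per group planned, each subject affected moves that group's proportion at or above 80% by 1/100 = 1 percentage point. The documents give no rate of non-return, so the number affected cannot be estimated.

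**The case against.** The best defence is that not crediting unverified tablets is a prespecified and conservative convention with little resting on it. No adherence-based analysis set is defined, SAP 4.2.2 rules out inferential statistics on adherence, and the subgroup is one of many exploratory ones. Delivery of treatment is also shown by duration of exposure, by the split of SVR12 by completed versus discontinued treatment, and by an accountability listing by subject and visit, in which a reader could examine individual cases. All of this stands, and it keeps the point small. It does not justify the rule, because crediting the last count uses the same evidence as for a returned bottle and still gives nothing for later doses.

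A second objection also stands: the documents do not say that interim counts are entered on the accountability CRF bottle by bottle, or whether a bottle counted at one visit and missing later is treated as not returned. The planned listing by visit suggests data at visit level but does not prove it. So it is not shown that the rule overrides counts already in the database.

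A reader might infer that the rule penalises the SOF+RBV arm more, since that arm takes two drugs. The documents do not support this. The rule names bottles, and each arm has three. RBV comes in blister packs, for which the SAP gives no rule. An excess appears only if the rule is extended to packs, the arm has six containers against three, and losses are not fully linked. With independent losses, 1 − (1 − q)³ against 1 − (1 − q)⁶ gives 3.0% against 5.9% of subjects at an assumed q of 1%, 5.9% against 11.4% at 2%, and 14.3% against 26.5% at 5%. The container count, the independence and q are all assumptions. If SOF and RBV are always lost together, the difference is zero.

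**Conclusion.** The point holds as a cheap improvement to descriptive and exploratory outputs. One unreturned bottle lowers a fully adherent subject's score to about 67% (64.3% to 71.4%) and always moves that subject below 80%. This rests on one bottle per dispensing and on all 84 doses having been taken.

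It would go too far to conclude that the SVR12-by-adherence display is worthless. How far it is distorted depends on how many bottles go unreturned, which is unknown. The below-80% group also mixes causes already, because the denominator is not shortened for subjects who stop early for reasons other than virologic failure. No difference between arms is established. The primary SVR12 analysis, made on the FAS regardless of adherence, is unaffected.

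**What to change.** Replace the sentence in SAP 4.2.2 with a rule of this content:
- For a container that is not returned, count the tablets taken as of the last visit pill count recorded for it.
- Where no count was recorded, keep zero, and flag those subjects in the adherence table.
- Apply the same rule to unreturned RBV blister packs, which the SAP does not now address.

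Keeping the never-counted subjects in the table and subgroup, but flagged, avoids the selection that excluding them would bring.

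First confirm that the accountability data hold interim counts by container. If they do not, the rule reduces to zero with a flag, which at least lets a reader see how many low scores come from unreturned containers. The change should be made before database finalization.

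The cost is a short SAP amendment, slightly more programming, and a slightly less conservative summary. The change removes most of the misclassification but not all: a fully adherent subject can still fall below 80% when the last count came early in the life of the bottle.

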#### **4.3. Protocol Deviations**

A summary of important protocol deviations will be provided by the Clinical Operations group for subjects in the Safety Analysis Set.

Subjects who received study drug other than their randomized treatment assignment will be listed with the start and stop dates that they received incorrect study drug.

## 5. BASELINE CHARACTERISTICS

### 5.1. Demographics

Subject demographic variables (ie, age, sex, race, and ethnicity) will be summarized by treatment group for both cohorts and total using descriptive statistics (n, mean, SD, median, Q1, Q3, minimum, and maximum) for age, and using the numbers and percentages of subjects for age categories (< 65 years,  $\geq$  65 years), sex, race, and ethnicity. Age is calculated in years at the date of initial study drug administration. If a subject did not receive study drug after randomization/enrollment, the subject's age will be calculated from the date that the subject signed the informed consent form. The summary of demographic data will be provided for the Safety Analysis Set.

A by-subject demographic listing, which includes the date the informed consent was signed, will be provided by subject ID number in ascending order.

### 5.2. Other Baseline Characteristics

Other baseline characteristics include:

- body mass index (BMI; in  $\text{kg}/\text{m}^2$ ) as a continuous variable and as categories ( $< 25 \text{ kg}/\text{m}^2$ ,  $\geq 25 \text{ kg}/\text{m}^2$ )
- HCV genotype subtype (if applicable)
- cirrhosis (cirrhosis, absence of cirrhosis, missing)
- IL28B (CC, non-CC; with non-CC further broken down to CT, TT)
- baseline HCV RNA ( $\log_{10}$  IU/mL) as a continuous variable and as categories ( $< 800,000 \text{ IU/mL}$ ,  $\geq 800,000 \text{ IU/mL}$ , and  $< 5 \log_{10} \text{ IU/mL}$ ,  $\geq 5 \log_{10} \text{ IU/mL}$ )
- baseline ALT (U/L) as a continuous variable and as categories ( $\leq 1.5 \times \text{ULN}$ ,  $> 1.5 \times \text{ULN}$ )
- prior HCV treatment experience (treatment-naive, treatment-experienced)
- most recent prior HCV treatment response (non-responder, relapse/breakthrough, early treatment discontinuation, met a virologic stopping rule, not otherwise listed, unknown) for treatment-experienced subjects
- estimated glomerular filtration rate (eGFR) using the Cockcroft-Gault equation

eGFR will be calculated by the Cockcroft-Gault method:  $\text{eGFR}_{\text{CG}} (\text{mL}/\text{min}) = [(140 - \text{age (yrs)}) \times \text{weight (kg)} \times (0.85 \text{ if female})] / (\text{serum creatinine (mg/dL)} \times 72)$ , where weight is total body mass in kilograms.

These baseline characteristics will be summarized for both cohorts by treatment group and total using descriptive statistics (n, mean, SD, median, Q1, Q3, minimum, and maximum) for continuous variables and using the numbers and percentages of subjects for categorical variables. The summary of baseline characteristics will be provided for the Safety Analysis Set.

A by-subject listing of other baseline characteristics will be provided by subject ID number in ascending order.

A separate by-subject data listing for cirrhosis determination and prior HCV treatment and response will be provided for all subjects at screening.

### **5.3.            Medical History**

General medical history data will not be coded, but will be listed only.

A by-subject listing of disease-specific medical history will be provided by subject ID number in ascending order.

## 6. EFFICACY ANALYSES

### 6.1. Primary Efficacy Endpoint

#### 6.1.1. Definition of the Primary Efficacy Endpoint

The primary efficacy endpoint is the proportion of subjects with SVR12, defined as HCV RNA < LLOQ (ie, < 15 IU/mL) 12 weeks after cessation of treatment. The primary analysis will be performed after all randomized/enrolled subjects have been followed through 12 weeks posttreatment or discontinued from study. The COBAS® AmpliPrep/COBAS® TaqMan® HCV Quantitative Test, v2.0 will be used to measure HCV RNA.

#### 6.1.2. Statistical Hypothesis for the Primary Efficacy Endpoint

In Cohort 1, the primary analyses will consist of a non-inferiority (NI) test of treatment LDV/SOF FDC for 12 weeks versus SOF+RBV for 12 weeks at the 0.05 significance level (two-sided). A clinically meaningful non-inferiority margin of 10% will be applied.

If we denote SVR12 rate for treatment group 1 (LDV/SOF for 12 weeks) as  $P_1$ , and SVR12 rate for treatment group 2 (SOF+RBV for 12 weeks) as  $P_2$ , the null and alternative hypotheses for non-inferiority for Cohort 1 are as follows:

$$H_0: P_1 - P_2 \leq -10\%$$

$$H_1: P_1 - P_2 > -10\%$$

In the primary efficacy analysis of Cohort 2, no statistical hypothesis testing will be performed.

#### 6.1.3. Primary Analysis of the Primary Efficacy Endpoint

In Cohort 1, the primary analyses will consist of a non-inferiority (delta=10%) of LDV/SOF for 12 weeks to SOF+RBV for 12 weeks at the 0.05 significance level (two-sided). Non-inferiority will be demonstrated (ie, non-inferiority null hypothesis will be rejected) if the lower bound of the two-sided 95% CI for the difference ( $P_1 - P_2$ ) in SVR12 is greater than -10%.

The two-sided 95% CI on the difference in SVR12 rates between the 2 treatment groups will be constructed based on stratum-adjusted MH proportions for the assessment of non-inferiority as follows {Koch 1989}:

$$P_1 - P_2 \pm Z_{(1-\alpha/2)} * SE(P_1 - P_2),$$

where

- $(P_1 - P_2) = \frac{\sum w_h d_h}{\sum w_h}$ , is the stratum-adjusted MH proportion difference, where  $d_h = p_{1h} - p_{2h}$  is the difference in the proportion of SVR12 of Treatment Groups 1 and Treatment Group 2 in stratum h (h=1 and 2).
- $w_h = \frac{n_{1h} n_{2h}}{n_{1h} + n_{2h}}$ , is the weight based on the harmonic mean of sample size per treatment group for each stratum where  $n_{1h}$  and  $n_{2h}$  are the sample sizes of Treatment Groups 1 and 2 in stratum h.
- $SE(P_1 - P_2) = \sqrt{\frac{\sum w_h^2 \left[ \frac{p_{1h}^*(1-p_{1h}^*)}{n_{1h}-1} + \frac{p_{2h}^*(1-p_{2h}^*)}{n_{2h}-1} \right]}{(\sum w_h)^2}}$ , where  $p_{1h}^* = \frac{m_{1h} + 0.5}{n_{1h} + 1}$  and  $p_{2h}^* = \frac{m_{2h} + 0.5}{n_{2h} + 1}$  and  $m_{1h}$  and  $m_{2h}$  are the number of SVR12 in Treatment Groups 1 and 2 in stratum h.
- $\alpha = 0.05$  for this study
- $Z_{(1-\alpha/2)} = Z_{0.975} = 1.96$  is the 97.5th percentile of the normal distribution

If the computed lower confidence bound is less than -1, the lower bound is defined as -1. If the computed upper confidence bound is greater than 1, then the upper bound is defined as 1.

The two-sided 95% exact CI based on binomial distribution (Clopper-Pearson method) will be provided for the SVR12 rate for each treatment group in Cohort 1 {Clopper 1934}.

In the primary efficacy analysis of Cohort 2, the SVR12 rate will be calculated along with two-sided 95% exact CI using Clopper-Pearson method.

#### 6.1.4. Subgroup Analysis of the Primary Efficacy Endpoint

Point estimates and 95% exact CIs of the SVR12 rates for each treatment group in each cohort, and of the difference (Group 1 – Group 2) in SVR12 rates will be displayed for each subgroup outlined in Section 3.4 for cohort 1.

The two-sided 95% exact CI based on Clopper-Pearson method will be provided for the SVR12 rate within each treatment group and subgroup. CIs on the difference of SVR12 rates within each subgroup will be constructed based on the standardized statistic and inverting two 1-sided tests {Chan 1999}.

A Forest Plot will graphically present point estimates and the two-sided 95% exact CIs on the treatment differences (Group 1 – Group 2) in SVR12 rates for each of the subgroups for Cohort 1.

## **6.2. Secondary Efficacy Endpoints**

### **6.2.1. Definition of Secondary Efficacy Endpoints**

Secondary efficacy endpoints include the following:

- The percentage of subjects with HCV RNA < LLOQ 4 and 24 weeks after discontinuation of treatment (SVR 4 and SVR 24)
- The percentage of subjects with HCV RNA < LLOQ while on treatment by study visit
- HCV RNA ( $\log_{10}$  IU/mL) and change from baseline in HCV RNA ( $\log_{10}$  IU/mL) through end of treatment (EOT)
- The percentage of subjects with virologic failure as the following:

#### **On-treatment virologic failure**

- HCV RNA  $\geq$  LLOQ after having previously had HCV RNA < LLOQ, while on treatment, confirmed with 2 consecutive values (note, second confirmation value can be posttreatment), or last available on-treatment measurement with no subsequent follow-up values (ie, breakthrough)
- 1  $\log_{10}$  IU/mL increase in HCV RNA from nadir while on treatment, confirmed with 2 consecutive values (note, second confirmation value can be posttreatment), or last available on-treatment measurement with no subsequent follow-up values (ie, rebound)
- HCV RNA persistently  $\geq$  LLOQ through 8 weeks of treatment (ie, nonresponse)

#### **Relapse**

- HCV RNA  $\geq$  LLOQ during the posttreatment period having achieved HCV RNA < LLOQ at end of treatment, confirmed with 2 consecutive values or last available posttreatment measurement
- Characterization of HCV drug resistance substitutions at baseline, during, and after therapy with LDV/SOF and SOF+RBV

## 6.2.2. Analysis Methods for Secondary Efficacy Endpoints

For analyses of HCV RNA < LLOQ by visit while on treatment and during the posttreatment (SVR) follow-up period, subjects will be assigned a value at each visit based on the analysis visit windows specified in Section 3.8.2. Missing values will be imputed based on the categorical imputation rules described in Section 3.6.1. The two-sided 95% exact confidence interval based on Clopper-Pearson method will be provided for the percentage of subjects with HCV RNA < LLOQ at each visit in each treatment group. The overall category for “HCV RNA < LLOQ” will be split into the following 2 subcategories: “< LLOQ TND” for subjects with target not detected and “< LLOQ detected” for subjects with < LLOQ detected in tabular displays.

Graphs for the percentage of subjects with HCV RNA < LLOQ over time during treatment will be displayed.

Summary statistics will be presented for absolute values and change from baseline in HCV RNA ( $\log_{10}$  IU/mL) by visit through EOT. Imputation rules described in Section 3.6.1 will be used to assign HCV RNA values for missing values at a visit that are bracketed by “< LLOQ TND” and/or “< LLOQ detected”. Otherwise, a missing = excluded analysis will be performed. Plots of the mean  $\pm$  SD and median (Q1, Q3) of absolute values and changes from baseline in HCV RNA through EOT will be presented.

[figure not shown]
For the SVR12 endpoint analysis, a summary table of the number and percentage of subjects with SVR12, virologic failure (VF), and Other will be created. All subjects who achieve SVR12 will be categorized as SVR12. Virologic failure will be descriptively summarized as “on-treatment virologic failure” and relapse (which will be broken down by study drug completed yes/no). Subjects who do not achieve SVR12 and do not meet criteria for VF will be categorized as “Other”. The denominator for relapse will be the number of subjects who had HCV RNA < LLOQ on their last observed on-treatment HCV RNA measurement; otherwise, the denominator will be the number of subjects in the FAS.

A concordance table between SVR12 and SVR24 will be provided for each treatment group in each cohort. Subjects with both observed SVR12 and observed SVR24 data will be included for this analysis.

Drug resistant substitutions will be analyzed as part of the Virology Study Report.

